6.3.1 Response Criteria

The table below shows the 2006 International Working Group response criteria for altering the natural history of MDS,[\[115\]](#) with modified definitions for HI-E, HI-P, and HI-N in the suggested 2018 International Working Group response criteria.[\[85\]](#)

Category	Response criteria (responses must last at least 4 weeks)
Complete remission	
 • Bone marrow: $\leq 5\%$ myeloblasts with normal maturation of all cell lines* • Persistent dysplasia will be noted* • Peripheral blood† 
 • Hgb ≥ 11 g/dL • Platelets $\geq 100 \times 10^9/L$ • Neutrophils $\geq 1.0 \times 10^9/L$ • Blasts 0%
Partial remission	All CR criteria if abnormal before treatment except: 
 • Bone marrow blasts decreased by $\geq 50\%$ over pretreatment but still $> 5\%$ • Cellularity and morphology not relevant
Marrow CR	
 • Bone marrow: $\leq 5\%$ myeloblasts and decrease by $\geq 50\%$ over pretreatment • Peripheral blood: if HI responses, they will be noted in addition to marrow CR

Stable disease	Failure to achieve at least PR, but no evidence of progression for >8 wks
Failure	Death during treatment or disease progression characterized by worsening of cytopenias, increase in percentage of bone marrow blasts, or progression to more advanced MDS FAB subtype than pre-treatment
Relapse after CR or PR	At least 1 of the following: 
 Return to pre-treatment bone marrow blast percentage Decrement of $\geq 50\%$ from maximum remission/response levels in granulocytes or platelets Reduction in Hgb concentration by ≥ 1.5 g/dL or transfusion dependence
Cytogenetic response	Complete 
 Disappearance of the chromosomal abnormality without appearance of new ones Partial 
 At least 50% reduction of the chromosomal abnormality
Disease progression	For participants with: 
 Less than 5% blasts: $\geq 50\%$ increase in blasts to $>5\%$ blasts 5%-10% blasts: $\geq 50\%$ increase to 10% blasts 10%-20% blasts: $\geq 50\%$ increase to $>20\%$ blasts 20%-30% blasts: $\geq 50\%$ increase to $>30\%$ blasts Any of the following: 
 At least 50% decrement from maximum remission/response in granulocytes or platelets Reduction in Hgb by ≥ 2 g/dL Transfusion dependence
Survival	Endpoints: 
 Overall: death from any cause Event free: failure or death from any cause PFS: disease progression or death from MDS DFS: time to relapse Cause-specific death: death related to MDS

MDS, myelodysplastic syndromes; Hgb, hemoglobin; CR, complete remission; HI, hematologic improvement; PR, partial remission; FAB, French-American-British; AML, acute myeloid leukemia; PFS, progression-free survival; DFS, disease-free survival.

To convert hemoglobin from grams per deciliter to grams per liter, multiply grams per deciliter by 10.

*Dysplastic changes should consider the normal range of dysplastic changes.

†In some circumstances, protocol therapy may require the initiation of further treatment (eg, consolidation, maintenance) before the 4-week period. Such participants can be included in the response category into which they fit at the time the therapy is started. Transient cytopenias during repeated chemotherapy courses should not be considered as interrupting durability of response, as long as they recover to the improved counts of the previous course.

Hematologic Improvement

Category	Participant pre-trial baseline	Response criteria
----------	--------------------------------	-------------------

Erythroid response (HI-E)	No Transfusion Dependence at baseline (0 RBC transfusions in 16 weeks)	At least 2 consecutive Hgb measurements ≥ 1.5 g/dL for a period of minimum 8 weeks in an observation period of 16 to 24 weeks compared with the lowest mean of 2 Hgb measurements (apart from any transfusion) within 16 weeks before treatment onset; only a response duration of at least 16 weeks, however, is considered clinically meaningful
	Low Transfusion Dependence at baseline (3-7 RBC transfusions in 16 weeks in at least 2 transfusion episodes, maximum 3 in 8 weeks)	Transfusion independence, defined by the absence of any transfusions for at least 8 weeks in an observation period of 16-24 weeks with the same transfusion policy compared with 16 weeks prior to treatment; only a response duration of at least 16 weeks, however, is considered clinically meaningful
	High Transfusion Dependence at baseline (≥ 8 RBC transfusions in 16 weeks, ≥ 4 transfusion episodes in 8 weeks)	
Major response
 
Transfusion independence, defined by the absence of any transfusions over a period of minimum 8 weeks in an observation period of 16-24 weeks with the same transfusion policy compared with 16 weeks prior to treatment; only a response duration of at least 16 weeks, however, is considered clinically meaningful

		
Minor response
 
Transfusion independence, defined by the absence of any transfusions over a period of minimum 8 weeks in an observation period of 16-24 weeks with the same transfusion policy compared with 16 weeks prior to treatment; only a response duration of at least 16 weeks, however, is considered clinically meaningful

Platelet response (HI-P)	Pre-treatment PLT $<100 \times 10^9/L$	
 Absolute increase of $30 \times 10^9/L$ for participants starting with $>20 \times 10^9/L$ PLTs 
or
 
 Increase from $<20 \times 10^9/L$ to $>20 \times 10^9/L$ and by at least 100% 
In addition:

		
 • In addition, evolution of bleeding symptoms is to be taken into account • Increments of platelets also for participants with a pre-treatment PLT count of $\geq 100 \times 10^9$ are to be reported
Neutrophil response (HI-N)	Pre-treatment ANC $<1.0 \times 10^9/L$	
 • At least 100% increase and an absolute increase $>0.5 \times 10^9/L$ • Increments of neutrophils also for participants with a pre-treatment ANC of $\geq 1.0 \times 10^9/L$ are to be reported

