A conceptual model of MDS evolution[11] presumes an initiating somatic driver mutation in the hematopoietic stem cell with subsequent formation of the mutant stem cell clone. The most commonly affected genes involve RNA splicing, DNA methylation, histone modification, transcription regulators, DNA-repair control, signaling and cohesin complex. Six genes are commonly affected and have been reported to be mutant in at least 10% of participants: *SF3B1*, *TET2*, *SRSF2*, *DNMT3A*, *ASXL1*, and *RUNX1*.[12] In the second phase, the mutant clone expands and when it reaches approximately 4% of the total hematopoiesis, clonal hematopoiesis of indeterminate potential (CHIP) arises. The duration of the first phase and potential of further progression to the third phase (MDS or clonal cytopenia of undetermined significance [CCUS] – cytopenia with presence of a clonal population without morphologic evidence of dysplastic changes) seems to be related to the genes affected by mutations and the size of the clonal population.[13] Most participants with CHIP and mutations in *DNMT3A*, *TET2*, or *ASXL1* will slowly progress to the third phase, while those harboring spliceosome gene mutations (i.e. *SF3B1*, *SRSF2*, *U2AF1*) will usually progress faster into MDS.[13] The spliceosome gene mutations are collectively present in more than 50% of the participants with MDS and are mutually exclusive.[14, 15] They are most commonly present in MDS participants when compared to the participants with other malignancies. In the third phase, clonal predominance of the mutant clone is established with further acquisitions of additional mutations (median of 3).[16, 17] The fourth phase is initiated with the selection of a clone that usually harbors AML-driving mutations (i.e. *FLT3*, *PTPN11*, *WT1*, *IDH1*, *NPM1*, *IDH2* and *NRAS*) leading to progression into secondary AML (s-AML) with $\geq 20\%$ blasts in the bone marrow (Figure 1).

According to World Health Organization (WHO) 2016 classification of myeloid neoplasms and acute leukemia,[1] based on the number of lineages affected by dysplastic changes, the percentage of blasts in bone marrow, the existence of ring sideroblasts and genetic changes, several different MDS-related entities can be discriminated (Figure 1) with defined diagnostic criteria. Apart from that, MDS precursor conditions, such as CHIP and CCUS, are defined (Figure 1) by expert panels through a consensus process.[18-21]

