2 ELIGIBILITY ASSESSMENT AND ENROLLMENT

2.1 ELIGIBILITY CRITERIA

2.1.1 Inclusion Criteria

1. Participants must have histologically or cytologically confirmed MDS according to 2016 WHO criteria[1]
 - a. And:
2. have HR-MDS (R-IPSS ≥ 3.5) and received a minimum of 2 and maximum of 8 prior cycles for phase I and 4 for phase II of DNMTi therapy, or
3. have LR-MDS (R-IPSS <3.5),
 - a. and, at least one cytopenia:
 - i. granulocytes $< 1.0 \times 10^9/L$ and/or
 - ii. hemoglobin $< 110 \text{ g/L}$ with signs/symptoms of symptomatic anemia or transfusion-dependency
 - iii. platelets $< 100 \times 10^9/L$

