6.3 RESPONSE CRITERIA

In addition to a baseline bone marrow biopsy, bone marrow biopsy samples from the participant's previous biopsy procedures will be requested from outside institutions: a formalin-fixed paraffin-embedded (FFPE) block or 10 unstained slides from initial MDS diagnosis, and an FFPE block from the most recent MDS biopsy prior to the participant arriving at NCI. These archival samples will be used to reconfirm the MDS diagnosis by NIH pathology department.

Participants will be assessed for response by standard response criteria for MDS.[\[85\]](#) For the purposes of this study, participants will be re-evaluated for response after each cycle by CBC with differential to assess for improvement in cytopenias and by protocol-defined time points for bone marrow evaluation. If results from interim bone marrow assessment demonstrate progression of disease (as defined by an increase in the number of malignant cells or blasts when compared to pre-treatment bone marrow examination or worsening cytopenias by amounts as defined below in section [6.3.1](#)), the subject will be taken off study.

Participants with ECOG performance status of 0-2 who fail to achieve a CR but have achieved a PR, SD, or hematologic improvement will be eligible for receive additional therapy if no other contraindications to further treatment.

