14.2.2 Toxicity

Fatal and serious myelosuppression and infectious complications can occur. Can cause fetal harm. Most common adverse reactions (incidence $\geq 20\%$) are fatigue, constipation, hemorrhage, myalgia, mucositis, arthralgia, nausea, dyspnea, diarrhea, rash, dizziness, febrile neutropenia, edema, headache, cough, decreased appetite, upper respiratory tract infection, pneumonia, and transaminase increased. The most common Grade 3 or 4 laboratory abnormalities ($\geq 50\%$) were leukocytes decreased, platelet count decreased, neutrophil count decreased, and hemoglobin decreased. [\[105, 118, 119\]](#)

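### Applied as written, the disease-progression row scores baseline transfusion dependence and transient haemoglobin falls as PFS events, and leaves out some transformations to AML

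*Combined protocol and SAP*

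**What the plan says.** The disease-progression row in 6.3.1 and Appendix D has two parts. The first sets blast rules by baseline band, each requiring a relative rise of at least 50%; in the 10%-20% band the level must also exceed 20%. The second is a list in which any one item suffices:

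- "At least 50% decrement from maximum remission/response in granulocytes or platelets";
- a haemoglobin fall of at least 2 g/dL, with no reference value or duration;
- "transfusion dependence", with no baseline comparison.

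Other provisions bear on this row:

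- **Entry (2.1.1).** An LR participant can qualify on haemoglobin "with signs/symptoms of symptomatic anemia or transfusion-dependency".
- **Response (6.3.1).** The HI-E table has rows for low and for "High Transfusion Dependence at baseline", so dependent participants are expected and can respond.
- **DNMTi (14.2.2).** "The most common Grade 3 or 4 laboratory abnormalities", at 50% or more, include decreased haemoglobin, platelets and neutrophils.
- **Footnote (6.3.1).** "Transient cytopenias during repeated chemotherapy courses should not be considered as interrupting durability of response". This concerns responses, not progression.
- **AML (1.2.1).** Clonal selection is described as "leading to progression into secondary AML (s-AML) with" at least 20% marrow blasts.
- **Endpoints (10.4.3).** PFS is progression or death from MDS. LFS is AML or death from any cause. The overall improvement rate includes stable disease, which 6.3.1 defines by absence of progression. PFS is reported as a Kaplan-Meier median with a 95% confidence interval, by cohort.

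**The concern.** A progression rule should separate a worsening participant from an unchanged one. One item here can be satisfied by the participant's condition at enrolment, and another by a short-lived effect of the backbone drug. The blast rule, meanwhile, can leave out transformation to AML. PFS would then partly reflect who was enrolled and how DNMTi affects counts. Stable disease, and with it the overall improvement rate, would be denied to unchanged participants who entered transfusion-dependent. If the rule is left open until scoring, whoever scores must choose a baseline convention in an open-label, single-arm setting after seeing the data.

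**Working it through.** The plan gives no assumed PFS, so there is no figure of its own to reproduce. The check compares the rules with each other and works out what follows.

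**1. Transfusion dependence.** The same table states a reference elsewhere: partial remission, marrow CR and failure refer to pre-treatment, and HI-E to the 16 weeks before treatment. This item states none. Appendix F records dependence on treatment as dependent or independent, with no cut-off and no change rule, so data collection does not supply the comparison.

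Let f be the share of LR participants dependent at entry. If each is an event at the first assessment, the Kaplan-Meier estimate there is at most S = 1 − f. The documents do not give f; 30% to 60% is assumed for illustration.

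- f = 30%: S is at most 0.70.
- f = 60%: S is at most 0.40.
- 12 of 25 dependent: S = 13/25 = 0.52, so the median falls later.
- 13 of 25 dependent: S = 12/25 = 0.48, so the median is the first assessment date.

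The binomial probability that at least 13 of 25 are dependent is 0.003, 0.154, 0.50 and 0.846 for a true share of 25%, 40%, 50% and 60%.

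**2. Haemoglobin.** The item needs only a fall of at least 2 g/dL, with no stated starting point and no repeat measurement. Section 14.2.2 lists decreased haemoglobin among the common grade 3 or 4 abnormalities on decitabine and cedazuridine, and the transient-cytopenia footnote does not reach this row. A transient on-treatment fall in the HR cohort can therefore score as progression. How often cannot be derived: 14.2.2 reports grades rather than falls in g/dL, and participants who have already had DNMTi may start from a lowered value.

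**3. Blasts and AML.** For baseline b between 10% and 20%, blast progression needs a level above 20% and at least 1.5 × b. AML needs at least 20%. The rules part when 1.5 × b exceeds 20, that is b > 20/1.5 = 13.3%.

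| Baseline | Progression from (1.5 × b) | AML but not blast progression |
|---|---|---|
| 14% | 21% | 20% to below 21% |
| 15% | 22.5% | 20% to below 22.5% |
| 16% | 24% | 20% to below 24% |
| 18% | 27% | 20% to below 27% |

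Example: 16% to 22% is a rise of 6/16 = 37.5%. That is AML and an LFS event, but not blast progression. From 10% to 13.3% the rules differ only at exactly 20%. Below 10% there is no gap, since reaching 20% more than doubles the baseline.

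**4. Removal provisions.** Section 6.3 acts on "an increase in the number of malignant cells or blasts when compared to pre-treatment bone marrow examination", or on worsening cytopenias by the amounts in 6.3.1, and takes the participant off study. Section 6.3.1 sets blast thresholds. Section 3.8.1 makes progressive disease a reason to stop protocol therapy, and 3.8.2 does not list it as an off-study criterion. These four provisions do not agree.

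**The case against.** The best defence is that progression implies change. Section 6.3 speaks of worsening cytopenias, the failure row ties progression to worsening, and the HI-E rows for dependent participants would be pointless if those participants had already progressed. The table is also presented as the published working-group criteria. This makes a change-from-baseline reading the likely intention, and it lowers the severity. It does not settle the scoring: no text says so for this item, and 6.3 refers back to 6.3.1 for the amounts.

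A reader might also infer more than the documents support:

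- *That DNMTi neutropenia and thrombocytopenia would generally count as progression.* That item is measured from maximum remission or response, so a non-responder does not meet it literally. For non-responders the concern rests on haemoglobin alone.
- *That the removal trigger misses AML.* The 6.3 wording covers any blast increase and would catch it. The gap is in PFS scoring, and another item in the row may still capture the case.
- *That this defect is what allows PFS to exceed LFS.* A death from another cause already does that, because PFS counts only death from MDS.
- *That the primary response rate is directly lowered.* The response in 10.2 is CR, PR, or marrow CR with HI, so transfusion independence alone does not count. Early removal could prevent the HI needed for marrow CR with HI, but that is indirect and the documents give no rate for it.
- *That counting error under the 6.3 wording would often signal progression.* Any rate depends on an assumed cell count, and on reading the reference to 6.3.1 amounts as not governing the blast part.

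**Conclusion.** The concern holds for three parts of the row. Unqualified transfusion dependence makes literal PFS events of participants whom the entry criteria admit, and it fixes LR median PFS at the first assessment if at least 13 of 25 are dependent at entry. That result depends on a literal reading and on a share the documents do not state. The haemoglobin item can score a transient fall on treatment in the HR cohort, at a frequency that cannot be derived. The blast rule leaves out AML for some participants with baseline blasts above 13.3% and below 20%; this is a narrow group, and LFS still counts the event. PFS, stable disease and the overall improvement rate are affected directly, the primary response rate only indirectly. Severity is should-fix: PFS is a secondary endpoint reported without a test, and 10.2 names overall survival as the most important secondary endpoint.

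**What to change.** For endpoint scoring only, in 6.3.1 and Appendix D:

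- **(a)** Count transfusion dependence as progression only when it is new relative to baseline. Match the pre-treatment window to the history collected: HI-E uses 16 weeks and Appendix F collects 3 months, so align them. Participants dependent at entry could then progress only through the other items; the plan should say whether that is intended.
- **(b)** State the reference value for the haemoglobin fall and require that it persist at a repeat assessment. Leave the granulocyte and platelet item anchored to maximum response.
- **(c)** Count transformation to AML (at least 20% blasts) as a PFS event whatever the relative rise.

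Separately, the sponsor must reconcile 6.3, 6.3.1, 3.8.1 and 3.8.2 on what counts as progression and whether it ends therapy or study participation. No removal rule is proposed here.

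The cost is wording in 6.3.1 and Appendix D, and in Appendix F if the transfusion window is lengthened; no new assessments are needed. Some haemoglobin-based progressions will be dated one visit later. The change should be made before any PFS scoring, so that the baseline rule is not chosen after the data are seen.

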6.4 TOXICITY CRITERIA

The following adverse event management guidelines are intended to ensure the safety of each participant while on the study. The descriptions and grading scales found in the revised NCI Common Terminology Criteria for Adverse Events (CTCAE) version 5.0 will be utilized for AE reporting. All appropriate treatment areas should have access to a copy of the CTCAE version 5.0. A copy of the CTCAE version 5.0 can be downloaded from the CTEP web site (http://ctep.cancer.gov/protocolDevelopment/electronic_applications/ctc.htm).

7 NIH REPORTING REQUIREMENTS / DATA AND SAFETY MONITORING PLAN

7.1 DEFINITIONS

Please refer to definitions provided in Policy 801: Reporting Research Events found at: <https://irbo.nih.gov/hrpp-policy-guidelines/>.

7.2 OHSRP OFFICE OF COMPLIANCE AND TRAINING / IRB REPORTING

7.2.1 Expedited Reporting

Please refer to the reporting requirements in Policy 801: Reporting Research Events and Policy 802 Non-Compliance Human Subjects Research found at: <https://irbo.nih.gov/hrpp-policy-guidelines/>. Note: Only IND Safety Reports that meet the definition of an unanticipated problem will need to be reported per these policies.

7.2.2 IRB Requirements for PI Reporting at Continuing Review

Please refer to the reporting requirements in Policy 801: Reporting Research Events found at: <https://irbo.nih.gov/hrpp-policy-guidelines/>.

7.3 NCI CLINICAL DIRECTOR REPORTING

Problems expeditiously reviewed by the OHSRP in the NIH eIRB system will also be reported to the NCI Clinical Director/designee; therefore, a separate submission for these reports is not necessary.

In addition to those reports, all deaths that occur within 30 days after receiving a research intervention should be reported via email unless they are due to progressive disease.

To report these deaths, please send an email describing the circumstances of the death to [contact] within one business day of learning of the death.

7.4 NIH REQUIRED DATA AND SAFETY MONITORING PLAN

7.4.1 Principal Investigator/Research Team

The clinical research team will meet on a regular weekly basis when participants are being actively treated on the trial to discuss each participant. Decisions about dose level enrollment and dose escalation if applicable will be made based on the toxicity data from prior participants.

All data will be collected in a timely manner and reviewed by the principal investigator or a lead associate investigator. Events meeting requirements for expedited reporting as described in section [7.2.1](#) will be submitted within the appropriate timelines.

The principal investigator will review adverse event and response data on each participant to ensure safety and data accuracy. The principal investigator will personally conduct or supervise the investigation and provide appropriate delegation of responsibilities to other members of the research staff.

8 SPONSOR PROTOCOL/SAFETY REPORTING

8.1 DEFINITIONS

8.1.1 Adverse Event

Any untoward medical occurrence in a participant or clinical investigation subject administered a pharmaceutical product and which does not necessarily have a causal relationship with this treatment. An adverse event (AE) can therefore be any unfavorable and unintended sign (including an abnormal laboratory finding), symptom, or disease temporally associated with the use of a medicinal (investigational) product, whether or not related to the medicinal (investigational) product. (ICH E6 (R2))

8.1.2 Serious Adverse Event (SAE)

An adverse event or suspected adverse reaction is considered serious if in the view of the investigator or the sponsor, it results in any of the following:

- Death
- A life-threatening adverse event (see section [8.1.3](#))
- Inpatient hospitalization or prolongation of existing hospitalization
 - A hospitalization/admission that is pre-planned (i.e., elective or scheduled surgery arranged prior to the start of the study), a planned hospitalization for pre-existing condition, or a procedure required by the protocol, without a serious deterioration in health, is not considered a serious adverse event.
 - A hospitalization/admission that is solely driven by non-medical reasons (e.g., hospitalization for participant or subject convenience) is not considered a serious adverse event.

- Emergency room visits or stays in observation units that do not result in admission to the hospital would not be considered a serious adverse event. The reason for seeking medical care should be evaluated for meeting one of the other serious criteria.
- Persistent or significant incapacity or substantial disruption of the ability to conduct normal life functions
- A congenital anomaly/birth defect
- Important medical events that may not result in death, be life-threatening, or require hospitalization may be considered a serious adverse drug experience when, based upon appropriate medical judgment, they may jeopardize the participant or subject and may require medical or surgical intervention to prevent one of the outcomes listed in this definition.

